1.2.2.1 Preclinical toxicology

In mice, the LD₅₀ was determined to be about 2000 mcg/kg (6000 mcg/m²) of body weight. This dose is higher than the 100 mcg/kg of body weight that was found to be lethal in some dogs (2000 mcg/m²) and monkeys (1200 mcg/m²) (25). However, the drug was found to be essentially non-toxic in dogs and monkeys administered at a dose of 24-50 mcg/kg/day (480-1000 mcg/m² dog, 288-600 mcg/m² monkey) intravenously for 24 consecutive days (25). The most frequently encountered toxicities at higher doses were bleeding, anorexia, vomiting, elevated liver function tests, electrolyte abnormalities, bone marrow suppression and azotemia (25).

In our experience in mice, doses of 1 mg/kg/day three times a week for 6 weeks delivered via intraperitoneal injection was essentially non-toxic to the mice. At necropsy, the mice treated at this dose and schedule had mild hypoalbuminemia, slightly increased ALT/AST with some evidence of liver toxicity described as mild to moderate and minimal thrombocytopenia.

It is notable that we were able to show that the drug interferes with the expression of the EWS-FLI1 downstream target NR0B1 in our mouse models at this 1 mg/kg/day dose. However, it is not clear if the dose of 25 mcg/kg/dose is high enough to interfere with EWS-FLI1 activity in patients. Therefore, one of the primary objectives will be to establish the inhibition of NR0B1 expression through mandatory tumor biopsies when feasible (see Section **Error! Reference source not found.**). These results will be critical for the interpretation of patient response to treatment, as

well as the future clinical development of mithramycin and the preclinical development of mithramycin analogs.

Administration of tritium labeled mithramycin to monkeys showed a terminal half-life of 5 hours. The peak cerebrospinal fluid concentration: plasma ratio was 0.12 and reached after 1 ½ hours (26). Preliminary pharmacokinetic parameters of ¹²⁵I-plicamycin (mithramycin) in human plasma using a radioimmunoassay were described (27). Three patients were studied and received mithramycin at a dose ranging from 0.85 to 1.0 mg/m² IV over 2 hours. Drug elimination was biphasic, with a mean elimination half-life of 10.6 hours (±1.7), and a clearance rate of 11.1± 0.4 ml/min/m².

1.2.3 Clinical studies in adults

Mithramycin underwent broad clinical evaluation in solid tumors and leukemias in the 1960's and was found to have some activity against leukemias, lymphomas and carcinomas. In particular, mithramycin was found to have activity against testicular cancer and was briefly used in the clinic for this tumor prior to the development of the currently used treatment regimen. However, a series of case reports in the literature suggest a particular sensitivity of Ewing sarcoma for mithramycin treatment. Prior clinical trials are summarized in Appendix 1.

The clinical experience with mithramycin is extensive as more than 1500 patients treated with mithramycin are reported in the literature. A formal Maximum Tolerated Dose (MTD) has not been established. However, the earliest reports of the drug efficacy at 50 mcg/kg/dose and therefore established this dose daily times 5 as the optimal treatment regimen (28). Subsequent to this report, a follow-up study of 58 patients found significant toxicity consisting of anorexia, nausea and vomiting at this dose and schedule in 70% of patients (29). As a result, the dose of drug used in most studies was 25 mcg/kg/day on various schedules. The recommended dose for the treatment of testicular cancer from the package insert from Pfizer was 25 mcg/kg/day daily times 7 (25). In addition, it was reported that significant toxicity is dose related and occurs at doses above 30 mcg/kg/dose (25). It is notable that the dose that led to the responses in the Ewing patients was 25 mcg/kg/day as a 8 to 24 hour infusion for 5-7 days (21).

In general, the most frequent toxicities observed were nausea, vomiting, elevated liver function tests, infusional fever, mucositis, bleeding tendencies, thrombocytopenia, electrolyte abnormalities, proteinuria and elevated BUN/Creatinine (summarized in (25)). Unfortunately, there was no systematic investigation of these toxicities and it is not clear the amount of supportive care these patients received. For example, nausea and vomiting occurred quite frequently, however, in at least two reports, the nausea responded to treatment with phenothiazines or other anti-emetics (30-32).

The most profound toxicity seen was hemorrhage. The tendency for bleeding occurred infrequently and in early reports was attributed to thrombocytopenia and accounted for 3 deaths out of 84 patients treated (33). Subsequent studies showed that bleeding occurred early in treatment at about day 4 and was dose related occurring in 5.4% of 1150 patients treated at 30 mcg/kg/day or less (25). This time frame is significantly shorter than what is typically seen for chemotherapy induced thrombocytopenia. In addition, it appears as though the platelet count remained >20,000/mcL in most of the cases of hemorrhage in the literature. Subsequent to these studies, it was determined that mithramycin treatment caused a decrease in coagulation factors II, V, VII and X (34). In addition, subsequent studies revealed that mithramycin causes abnormal platelet adhesion in the setting of a normal platelet count consistent with a platelet adhesion

molecule deficiency (35). It is notable, that in addition to inhibiting EWS-FLI1, mithramycin is known to inhibit the SP1 transcription which is known to drive the biosynthesis of coagulation factors as well as platelet adhesion glycoproteins. Nevertheless, in all the cases of hemorrhage reported in the literature, it is not clear if the patients were taking any anti-coagulation medications, what type of blood product support was provided, and how effective the blood product support was in that era of treatment. In particular, it is not clear if patients received platelets in the setting of a normal platelet count as would be required for an acquired platelet adhesion defect. Regardless of the etiology, this side effect must be approached with extreme caution.

Another rare but significant side effect described in the literature is the report of toxic epidermal necrolysis that has been associated with mithramycin treatment (36, 37). This side effect is reported in two separate case reports but was omitted in the package insert from Pfizer (37) and appears to begin with plethora and non-specific skin findings. The incidence of this side effect is unclear, however due to the substantial nature of this reaction, all skin eruptions should be approached with significant caution.

One report describes potentiation of the cardiotoxicity of anthracyclines with mithramycin treatment (38). However, this report provides no details of the cardiotoxicity observed and refers to mitomycin. No other mention of cardiotoxicity has been found in the literature, package insert or IND that was previously filed.

Finally, no report or investigation of cumulative toxicity could be found in the literature. The closest report is one of a long term follow-up of patients with testicular carcinoma treated with mithramycin (39). In this report 10 patients with metastatic testicular carcinoma out of 62 treated with mithramycin were available for long term follow up at 23 years. No long-term side effect of the drug is reported.

1.2.4 Clinical activity

In 1960, the first evaluation of more than 36 patients with a variety of tumor histologies found an overall response rate of just under 20% defined as tumor shrinkage, improvement in performance status or a leveling off of body weight (28). Subsequent to this, mithramycin was evaluated in a number of reports and activity was found in a variety of histologies although patient numbers and standard methods of evaluating responses were limited (31, 40-42). The tumor type that seemed to show a consistent response was testicular carcinoma. In one series of 305 patients with stage III testicular CA, 10% of patients achieved a complete response and an additional 25% showed some evidence of tumor regression (25). Many of these cases were durable responses in patients with widely metastatic disease. However, the overall response rate was low and the widespread use of the drug in this tumor, likely was limited by the development of the successful "Einhorn regimen" for the treatment of this cancer.

In addition to testicular carcinoma, mithramycin was used for the treatment of malignant hypercalcemia with 45% of patients responding to a single dose of mithramycin in one study (43). However, in the same report, the bisphosphonate pamidronate was far superior and ultimately replaced mithramycin in this setting. For similar reasons, mithramycin was investigated for the treatment of Paget's disease of bone where it was found to have good activity in the management of this disorder of osteoclasts. In one report, 10/10 patients with Paget's disease reported improvements in pain and an increase in overall activity with treatment (32).

The activity of mithramycin in Ewing sarcoma was impressive in some of the earliest reports of this drug in the clinic (33). A total of 5 patients with ESFT have been treated with mithramycin and reported in the literature (21). Of those 5 patients, 2 patients experienced widespread regressions of metastatic disease with mithramycin treatment as a single agent. One of the two patients had a durable completed response and was followed for more than 7 years (21). It is not clear why the drug was not further investigated in ESFT. It is likely that the advent of anthracycline based therapies and the evolution of combination therapies supplanted the interest of the community in alternative single agent therapies.

1.2.5 Clinical studies in children

No formal pediatric studies of mithramycin in children have been reported. Based on the literature available, only 5 patients under the age of 18 received mithramycin (40). In this published report of 26 patients, 5 children (ages 10-16 years of age) with embryonal carcinoma of the testis, malignant teratoma testis or Ewing sarcoma received total mithramycin doses of 185-250 mg/kg over 24 hours. No toxicity data was reported on these five study participants. One subject experienced a mixed response after the first course, one had regression of small metastases but no change in larger tumors, and one subject experienced transient improvement in pain reports. It is notable in this report that the patient with Ewing sarcoma that achieved a complete response was a 22 year-old adult.

1.3 RATIONALE SUMMARY

Our high throughput screen of more than 50,000 compounds identified mithramycin as an inhibitor of EWS-FLI1. ESFT has a strong dependence on EWS-FLI1 for cellular survival and we have shown that mithramycin interferes with this activity *in vitro* and *in vivo* and markedly suppresses ESFT xenograft growth. Responses to single agent mithramycin have also been described in patients with refractory ESFT, but the objective response rate of mithramycin in ESFTs has not been determined. These findings provide a strong rationale for the development of mithramycin in patients with EWS-FLI1 positive Ewing sarcoma.

In addition, mithramycin demonstrated activity in other adult solid tumors, and our preclinical data suggest that other pediatric solid tumors might also be sensitive to mithramycin treatment.

We therefore propose a broad phase I trial of mithramycin for children and adolescents with refractory solid tumors to confirm tolerability of mithramycin at the recommended dose for adults established in the 1960s. There will be a limited dose escalation to the adult recommended dose. At the adult recommended dose (or MTD) up to six children \leq 12 years of age and six children \geq 12 years of age will be enrolled to gain experience with the toxicities of mithramycin over a broad age range.

Simultaneous to enrolling children in the phase I portion of this trial, adults with EWS-FLI1 positive Ewing sarcoma will enroll on the phase II portion of the trial, which has the goal to determine the activity of mithramycin in EWS-FLI1 positive Ewing sarcoma. Initiating the phase II study in adults while determining the optimal dose in children, is based on extensive previous safety and dosing information obtained from clinical trials conducted in adults and the anecdotal reports of activity in patients with Ewing sarcoma treated in the past with mithramycin. The Phase II portion will be implemented in adults using the previously approved mithramycin dose of 25 microgram/kg administered over six hours once daily for 7 days to be repeated every 28 days.

Once the adult phase II dose has been determined safe in children and adolescents, children will also be accrued to the phase II portion. Should the pediatric phase II dose of mithramycin differ from the adult phase II dose, the protocol will be amended to address accrual and response rate to mithramycin in children in a separate stratum. The objective response rate of mithramycin will be determined in EWS-FLI1 positive Ewing sarcoma using a 2-stage design and targeting an objective response rate (RECIST PR and CR) of 25%.

2 ELIGIBILITY ASSESSMENT AND ENROLLMENT

2.1 ELIGIBILITY CRITERIA

2.1.1 Inclusion Criteria

2.1.1.1 Diagnosis

Patient's current disease state must be one for which there is no known curative therapy or therapy proven to prolong survival with an acceptable quality of life.

Phase I Portion: Measurable or evaluable refractory or recurrent extracranial solid tumors, excluding brain tumors and cerebral metastases.

Phase II Portion adults and children: Refractory or recurrent extracranial Ewing sarcoma with EWS-FLI1 fusion transcript. Patients enrolled to this cohort must have measurable disease. Presence of the transcript will be determined during histologic confirmation of disease with a CLIA approved EWS-FLI paraffin assay in the Laboratory of Pathology CCR, NCI, unless a pathology report documenting presence of the transcript using a CLIA approved assay is obtained from the referring institution.

2.1.1.2 Histologic confirmation of disease in the Laboratory of Pathology, CCR, NCI, NIH.

2.1.1.3 Age

Phase I Portion: \geq 12 months to \leq 17 years

Phase II Portion in adults initially: \geq 18 years

Phase II Portion expanded in pediatrics after determination of phase II dose in children will include children \geq 12 months to \leq 17 years

2.1.1.4 Performance Score: Karnofsky ($>$ 10-17 years old) or Lansky (\leq 10 years old) \geq 50%, or ECOG 1 or 2 (adults) (See Appendix 2)

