2.2 SCREENING EVALUATION

2.2.1 General

Pre-treatment blood test should be performed within 7 days and imaging studies within 2 weeks prior to enrollment on the trial unless otherwise stated. The evaluations required prior to starting treatment are listed in table form in Appendix 3 Study Calendar.

HISTORY AND PHYSICAL EXAMINATION: including documentation of height and weight (average of 3 measurements on the same day), measurable disease, vital signs (blood pressure, heart rate, respiratory rate, temperature), performance status, history of bleeding disorder, HIV, HBV, HCV, and signs and symptoms within one week of enrollment.

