2.3.1 Registration at NCI

Authorized staff must register an eligible candidate with NCI Central Registration Office (CRO) within 24 hours of signing consent. A registration Eligibility Checklist from the web site (<http://home.ccr.cancer.gov/intra/eligibility/welcome.htm>) must be completed and faxed to [contact]. After confirmation of eligibility at Central Registration Office, CRO staff will call pharmacy to advise them of the acceptance of the patient on the protocol prior to the release of any investigational agents. Verification of Registration will be forwarded electronically via e-mail to the research team. A recorder is available during non-working hours.

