3 STUDY IMPLEMENTATION

3.1 STUDY DESIGN

This study will be conducted as a single institution, open label Phase I/II trial of mithramycin. The Phase I portion will be conducted in children and adolescents (12 months to \leq 17 years of age) with refractory extracranial solid tumors. The cohort at the recommended dose or MTD will be expanded up to 12 patients, and attempts will be made to enroll at least 6 patients that are \geq 12 years of age and 6 patients that are $<$ 12 years of age to gain experience with a broad age range of patients.

In the phase II portion of the trial the adult dose (17.5 mcg/kg/dose) will be administered to patients with measurable refractory or recurrent Ewing sarcoma and EWS-FLI1 fusion transcript to determine the objective response rate (CR and PR) to mithramycin using RECIST criteria. Initially this portion of the trial will be open to eligible participants \geq 18 years of age. Enrollment will be expanded to include children and adolescents once safety at this dose is determined. If the pediatric phase II dose of mithramycin differs from the adult phase II dose, the protocol will be amended to address accrual and response rate to mithramycin in children in a separate stratum.

The Phase I and Phase II portions of the protocol will enroll patients simultaneously.

Patients with ESFT enrolled on this study (phase II portion) who meet eligibility criteria for tumor biopsies will undergo mandatory tumor biopsies to assess EWS-FLI1 target blockade by mithramycin (see [Appendix 7: Studies to be performed on tumor tissue](#)).

Mithramycin will be administered intravenously over 6 hours once daily for 7 days to be repeated every 28 days. Patients may continue to receive mithramycin for as long as they tolerate drug (Sections [3.1.1](#) and [3.4](#)) and do not have progressive disease (Section [6.2](#)).

Patients on study will be closely monitored for the development of toxicity including regular physical examinations, blood pressure monitoring, laboratory evaluations, and physical examinations with particular attention to the development of any signs of bleeding. Patients will be admitted to the hospital for the first treatment cycle during administration of mithramycin in order to allow for close monitoring of toxicities.

Disease will be monitored after every even treatment cycle using appropriate imaging studies using RECIST criteria.

Correlative studies are described in Section [5](#).

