11.2 APPENDIX 2: PERFORMANCE STATUS SCALES/SCORES

PERFORMANCE STATUS CRITERIA Karnofsky and Lansky performance scores are intended to be multiples of 10.					
ECOG (Zubrod)		Karnofsky		Lansky	
Score	Description	Score	Description	Score	Description
0	Fully active, able to carry on all pre-disease performance without restriction.	100%	Normal, no complaints, no evidence of disease.	100%	Fully active, normal.
		90%	Able to carry on normal activity; minor signs of symptoms of disease.	90%	Minor restrictions in physically strenuous activity.
1	Restricted in physically strenuous activity but ambulatory, able to carry out light or sedentary work, e.g., light housework, office work.	80%	Able to carry on normal activity with effort; some signs or symptoms of disease.	80%	Active, but tires more quickly.
		70%	Cares for self, unable to carry on normal activity or do active work.	70%	Both greater restriction of, and less time spent in, play activities.
2	Ambulatory and capable of all self-care but unable to carry out any work activities. Up and about more than 50% of waking hours.	60%	Requires occasional assistance but is able to care for most of own needs.	60%	Up and around, but minimal active play; keeps busy with quieter activities.
		50%	Requires considerable assistance and frequent medical care.	50%	Gets dressed, but lies around much of the day; no active play; able to participate in quiet play and activities.
3	Capable of only limited self-care, confined to bed or chair more than 50% of waking hours	40%	Disabled; requires special care and assistance.	40%	Mostly in bed; participates in quiet activities.
		30%	Severely disabled; hospitalization indicated, although death not imminent.	30%	In bed; needs assistance even for quiet play.
4	Completely disabled. Cannot carry on any self-care. Totally confined to a bed or chair	20%	Very ill; hospitalization necessary; active supportive treatment required.	20%	Often sleeping; play entirely limited to very passive activities.
		10%	Moribund, fatal process progressing rapidly	10%	No play; does not get out of bed
5	Dead	0%	Patient expired	0%	Unresponsive; Dead

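### Section 2.1.1.4 leaves ECOG 0 adults out of phase II, although the matching performance band is admitted for children and no reason is given

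*Combined protocol and SAP*

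**What the plan says.** Section 2.1.1.4 (Performance Score) has two parts. Patients under 18 need at least 50% on Karnofsky (over 10 to 17 years) or Lansky (10 years or younger). Adults are covered by "or ECOG 1 or 2 (adults"), followed by a pointer to Appendix 2. Because Karnofsky is tied to an age range that ends at 17, an adult cannot qualify through it.

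Appendix 2 sets the three scales side by side. ECOG 0 is described as "Fully active, able to carry on all pre-disease performance without restriction" and occupies the rows for 100% and 90%. Karnofsky 100% reads "Normal, no complaints, no evidence of disease", and Karnofsky 90% reads "Able to carry on normal activity; minor signs of symptoms of disease".

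On disease, section 2.1.1.1 says of the phase II group: "Patients enrolled to this cohort must have measurable disease".

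The screening list in section 2.2.1 includes "performance status, history of bleeding disorder" among the items to document, with no threshold. The study calendar (Appendix 3) likewise records a performance score without a limit.

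**The concern.** A performance-status criterion normally keeps out patients too unwell to tolerate treatment. Here the paediatric rule does that, while the adult rule also shuts out the fittest patients. Read literally, a 17-year-old at Karnofsky 90% meets section 2.1.1.4 and an 18-year-old of equivalent status, scored ECOG 0, does not.

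The wording is operative. Section 2.3.1 requires an eligibility checklist and says: "After confirmation of eligibility at Central Registration Office, CRO staff will call pharmacy". An ECOG 0 adult would be stopped at that step, or would be enrolled against the approved text. Section 7.1.8 makes any such departure a deviation, and section 7.2.1 requires all deviations to be reported within 7 working days. The waiver in section 7.2.4 covers timing windows only.

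The criterion applies to the group that opens phase II. Section 3.1 states: "Initially this portion of the trial will be open to eligible participants" aged 18 or over. Adults are also the only source of the paired biopsies in section 8.4, where at least 12 and up to 20 evaluable patients are wanted.

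**Working it through.** No figure in the plan is being recalculated. The check maps the two criteria in section 2.1.1.4 onto the rows of Appendix 2.

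| Appendix 2 band (Karnofsky/Lansky) | ECOG beside it | Children (floor 50%) | Adults (ECOG 1 or 2) |
|---|---|---|---|
| 90-100% | 0 | admitted | not listed |
| 70-80% | 1 | admitted | admitted |
| 50-60% | 2 | admitted | admitted |
| 30-40% | 3 | not admitted | not admitted |
| 10-20% | 4 | not admitted | not admitted |

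1. Lower limit: 50% is the bottom of the ECOG 2 band, so the two rules agree there.
2. Upper end: the paediatric rule has no ceiling, while the adult rule stops at ECOG 1. The difference is the ECOG 0 row alone.
3. Compatibility with disease: Karnofsky 100% is worded as absence of disease, which does not fit the disease requirement in section 2.1.1.1, so it is set aside. Karnofsky 90% allows for minor disease signs. ECOG 0 is defined by activity, not by absence of tumour, so an ECOG 0 adult can have measurable Ewing sarcoma. The comparison across age 18 therefore rests on Karnofsky 90% against ECOG 0. Lansky 100% applies only at 10 years or younger and is not needed.
4. Search for a reason: the précis, the biopsy criteria (2.1.1.11), the exclusions (2.1.2), screening (2.2.1), the subject-selection rationale (9.1) and the study calendar neither admit ECOG 0 adults nor explain the omission. The marrow and liver limits in section 2.1.1.6 bound only the impaired side, and exclusion 2.1.2.1 concerns illness that would reduce tolerance of treatment.
5. Effect on the design: the two-stage rule in section 8.2 (stop at 0 of 9; 3 or more of 24 for success) does not involve performance status. Its exact properties are an early-stopping probability of 0.95^9 = 0.630 and a type I error of 0.093 at a true rate of 5%, with power of 0.903 at 25%. These agree with the stated 63%, 10% and 10%, and they stay the same whether or not ECOG 0 adults are admitted.

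**The case against.** The strongest reply is that this is a small wording query. No power, alpha or sample-size figure moves, no bias is shown, and the accrual effect cannot be sized. Those points are correct, and they limit the weight of the finding.

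Appendix 2 is a reference scale that sets no eligibility, and nothing requires adult and paediatric limits to match. That also stands: the expectation of parity is an inference, though the exact match of the lower limits supports it.

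The descriptors overlap. Lansky 90% mentions minor limits on strenuous activity, which resembles ECOG 1, so an adult who fits a 90% description might be scored ECOG 1 and enter. The age-18 comparison therefore holds by row alignment rather than for every individual. It does not help an adult who is actually scored ECOG 0.

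The registration checklist is not among the documents, so practice may differ from the text. That makes the practical consequence uncertain but leaves the written criterion as it is.

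The biopsy argument is modest. Sections 3.1.3 and 8.4 keep enrolment open until 12 evaluable pairs are reached, and the stated limits on yield (accessibility, consent, baseline NR0B1 expression) are not linked to ECOG. For response, children may join once the dose is deemed safe, so that objective does not rest on adults alone.

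None of this supplies a reason for the omission or a passage that overrides it.

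**Conclusion.** The concern holds. As written, section 2.1.1.4 excludes ECOG 0 adults from phase II without explanation, while the corresponding band is open to patients up to 17. The discrepancy is a single adult score; on the Karnofsky scale used up to age 17, the one level in that band that fits the required disease is 90%. The conclusion rests on a literal reading of the criterion and on the row alignment in Appendix 2. A drafting slip is the likelier explanation, but the documents do not show intent. The number of adults affected is unknown, because no ECOG distribution is given and the checklist was not available. The criterion should be corrected or justified.

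**What to change.** Ask the sponsor to confirm what was intended. If the omission is a slip, reword the adult part of section 2.1.1.4 to ECOG 0, 1 or 2, which brings it into line with the paediatric floor and the Appendix 2 bands. If ECOG 0 adults were meant to be excluded, say so and give the reason in the same section. In either case, check that the registration eligibility checklist cited in section 2.3.1 carries the same wording.

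The text change is minimal, but it alters an inclusion criterion, so it needs a short amendment and IRB approval. Sample size, decision rule and analysis are untouched.
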